10 STUDY PROCEDURES

10.1 VISIT SCHEDULE

The visit schedule and procedures/assessments are listed in the Study Flow Chart ([Section 1.2](#)). The aim of this section is to provide details on how some of the procedures/assessments should be performed.

This is an out-patient study and consists of 12 on-site visits and 4 telephone visits, although optional on-site and/or telephone visits can be scheduled at any time for any reason during the study whenever considered necessary by the Investigator.

The patients need to be fasting for on-site visits Visit 1 through Visit 15 (Week -6 through Week 52), unless otherwise instructed by the Investigator. Throughout the study, “fasting” is defined as at least 8 hours without any food intake (except for water). **Note:** if the patient is not fasting at the visits specified above, the blood sample will not be collected and a new appointment should be given to the patient for the following day if possible, with instruction to be fasted (other procedures can be performed as scheduled). The first Run-in Visit (Visit 2) can be performed as soon as the results of all Screening tests are available and the patient is confirmed to be eligible for participation in the study. The visit window for Visit 5 is ± 2 days, and Visits 7 through 13 should occur within ± 3 days. Visits 14 and 15 should occur at the scheduled time point ± 7 days. Visit 15 (EOT) should occur from Day 357 to Day 371. For the Follow-up Visit (Visit 16), the visit should occur within a window of ± 3 days, 2 weeks after the last dose of IMP. If one date is changed, the next visit should occur according to the original schedule, ie, calculated from the date of Baseline Visit (Visit 6, Day 1).

For a complete list of procedures scheduled for each study visit, please refer to the Study Flow Chart ([Section 1.2](#)), which details the procedures to be performed.

All data obtained during the trial visits are reviewed by the Investigator and/or Sub-investigators who are qualified in the treatment of T2D and are trained on the study.

10.1.1 Screening Period

The Screening Period is up to 6 weeks in duration and includes the Screening phase and the Run-in phase.

10.1.1.1 Screening phase (Visit 1)

The Screening phase will be up to 2 weeks in duration and includes Visit 1 (Week -6) only. It must be long enough to collect the data to establish whether the patient satisfies the inclusion/exclusion criteria.

Patients will undergo Screening assessments at Visit 1 (Week -6) following signing of the ICF. Patients who meet the inclusion criteria as noted in [Section 7.1](#) and have no exclusion criteria as noted in [Section 7.2](#) will be randomized at Visit 6 (Day 1).

The IRT will be contacted at Visit 1 for notification of the Screening Visit and to obtain the patient number.

In cases where original screen failure was due to reasons expected to change at rescreening and based upon the Investigator's clinical judgment, the patient can be rescreened once prior to entering Run-in for this study. In these cases, a patient will need to sign a new ICF, be registered as a new patient in the IRT, and assigned a new patient number (first Screening Visit is to be registered as a screen failure in the IRT), and again complete the Screening Visit procedures/assessments.

10.1.1.1.1 On-site Visit 1 (Week -6) Screening Visit

The following procedures/assessments will be performed at Visit 1 (Week -6):

- Obtain the informed consent:
 - The patient will receive verbal information concerning the aims and methods of the study, its constraints and risks, and the study duration. Written information will be provided to the patient. Written informed consent must be given by the patient and Investigator prior to any investigations.
- [REDACTED]
- [REDACTED]
- IRT to be notified (allocation of ID, registration of Screening)
- Assessment of all inclusion/exclusion criteria
- Collection of demographic data (age, gender, race, and ethnic origin)
- Assessment of the patient's medical and surgical history: to include history of T2D, treatment, and complications (eye, kidney, amputations, etc); history of smoking/tobacco use; history of alcohol and drug abuse
- Concomitant medication and medication history, including any prior medications for T2D
- Complete physical examination including height, weight, and vital signs (SBP and DBP, temperature, heart rate, and respiratory rate). After 5 minutes resting, seated SBP, DBP, and heart rate will be assessed 3 times with at least 1 minute between each measurement (see [Appendix D](#) for details).
- Patient diary is dispensed and instructions/training are provided
- 12-lead ECG

- The following laboratory testing (by the central laboratory):
 - HbA1c
 - Safety laboratory, including amylase and lipase
 - Hematology
 - Serum pregnancy testing for WOCBP or serum FSH and estradiol (for women of nonreproductive potential if definition of postmenopausal or premenopausal cannot be satisfied; see [Appendix A](#))
 - Urinalysis (dipstick and microscopy)
- PRO: TRIM-D
- Patients are instructed to return to the site in the fasting state for Visit 2 (Week -4).

10.1.1.2 Run-in phase (Visits 2 to 5)

The Run-in phase is 4 weeks in duration and includes Visits 2 to 5 (Weeks -4 to -1, inclusive).

10.1.1.2.1 On-site Visit 2 (Run-in, Week -4)

The following procedures/assessments will be performed at Visit 2 (Week -4):

- Assessment of exclusion criteria
- Measurement of BW
- Abbreviated physical examination including vital signs (SBP, DBP, and heart rate). After 5 minutes resting, seated SBP, DBP, and heart rate will be assessed 3 times with at least 1 minute between each measurement (see [Appendix D](#) for details).
- Diet and exercise instruction
- Blood glucose and BHB meters are dispensed and instructions/training is provided
- Glucose test strips and BHB strips are dispensed
- IRT to be notified (registration of Run-in, allocation of single-blind placebo Run-in kit and Lantus kit)
- Instruction on DKA symptoms and glucose testing is provided
- Patient diary is collected and reviewed and a new one dispensed. Instructions/training are provided as needed.
- AEs/SAEs/AESI/EOSI and hypoglycemia occurring since Visit 1 (if any) are reported
- Run-in kit/placebo (IMP) and Lantus are dispensed
- Treatment with study provided Lantus is started either on evening of Visit 2 (if evening dose) or the following morning (if morning dose)
- Changes in concomitant medication are reported
- Fasting SMBG is assessed and Lantus dose adjustments are made as necessary

- Patients are instructed to return to the site for Visit 5.

10.1.1.2.2 Telephone Visits 3 and 4 (Run-in Weeks -3 and -2)

The following will be performed at this visit:

- Assessment of exclusion criteria
- Fasting SMBG is reviewed from diary and Lantus dose adjustments are made as necessary ([Section 8.2](#))
- AEs/SAEs/AESI/EOSI and hypoglycemia (if any) are reported
- Patients are instructed to return to the site for Visit 5.

10.1.1.2.3 On-site Visit 5 (Run-in, Week -1)

The following procedures/assessments will be performed at Visit 5 (Week -1):

- Assessment of exclusion criteria
- Measurement of BW
- Abbreviated physical examination including vital signs (SBP, DBP, and heart rate). After 5 minutes resting, seated SBP, DBP, and heart rate will be assessed 3 times with at least 1 minute between each measurement (see [Appendix D](#) for details).
- Diet and exercise instruction
- Instruction on DKA symptoms, glucose testing, and basic genitourinary (GU) hygiene and hydration (see [Appendix C](#)) is provided
- Patient diary is collected/reviewed. Instructions/training are provided as needed.
- IMP and Lantus accountability and compliance
- AEs/SAEs/AESI/EOSI and hypoglycemia (if any) are reported
- Changes in concomitant medication are reported
- Fasting SMBG is assessed and Lantus dose adjustments are made as necessary ([Section 8.2](#))
- Patients are instructed to return to the site in the fasting state for Visit 6 (Randomization)
- The following laboratory testing (by the central laboratory):
 - HbA1c
 - Clinical chemistry, including amylase and lipase.

10.1.2 Double-blind Treatment Period (Day 1 to Week 52)

Upon successful completion of the Run-in phase, patients will be randomly allocated to sotagliflozin 400 mg, sotagliflozin 200 mg, or placebo for the double-blind Treatment Period. All

randomized patients will be followed at regular on-site visits for the duration of the Treatment Period. Visit 7 (Week 2) and Visit 9 (Week 6) are telephone visits.

Patients will be instructed that their Lantus dose should remain unchanged ($< \pm 10\%$ of the randomization dose, or $< \pm 4$ units, whichever is less) until after Week 18 unless for safety reasons (eg, hypoglycemia, during treatment of an SAE) or meet the rescue criteria. After Week 18, Lantus dose may be adjusted if deemed necessary by the Investigator.

In addition to routine laboratory testing, the following will be performed at specified time points: plasma concentration, serum and capillary BHB, hematology, fasting lipids, urinalysis, complete physical examination, diet and exercise instruction, [REDACTED], PQAT, and TRIM-D.

The date and time of the last intake of IMP prior to visits where PK samples are taken should be recorded by the patient in the patient diary. Patients should be reminded of this at visits preceding PK time points to ensure these details are captured.

In the event of abnormal urinalysis findings suspicious of UTI, urine culture should be performed. Positive urine culture determination will be based upon the criteria of the reporting laboratory. Additionally, urine culture should be performed if at any point the Principal Investigator suspects the presence of a UTI.

10.1.2.1 On-site Visits 6, 8, 10, 11, 12, 13, and 14 (Weeks 0, 4, 8, 12, 18, 26, and 39)

The following procedures will be performed at these visits:

- Exclusion criteria are to be reviewed, including assessment of compliance during the Run-in phase (Visit 6 only)
- Randomization (Visit 6 only)
- Measurement of BW (all visits)
- Abbreviated physical examination including vital signs (SBP and DBP, and heart rate). After 5 minutes resting, seated SBP, DBP, and heart rate will be assessed 3 times with at least 1 minute between each measurement (see [Appendix D](#) for details) (all visits except Visit 13, where a complete physical examination will be performed).
- Concomitant medications are assessed (all visits)
- Glucose test strips and BHB strips are dispensed (all visits)
- Measurement of capillary BHB (all visits, except Visit 11)
- Diet and exercise instruction (Visits 6 and 13 only)
- Instruction on DKA symptoms, glucose testing, and basic GU hygiene and hydration (see [Appendix C](#)) is provided (all visits)
- IRT to be notified, IMP and Lantus for resupply (all visits)
- Patient diary is collected/ reviewed and new diary dispensed. Instructions/training are provided as needed (all visits).

- IMP and Lantus are dispensed (all visits)
- IMP and Lantus accountability and compliance (all visits)
- Fasting SMBG is assessed and Lantus dose adjustments are made as necessary (all visits)
- Record results of 7-point SMBG (Visits 6 and 12 only)
- Patients are evaluated for glycemic rescue (see [Section 9.1.4.7](#)) (all visits)
- AEs/SAEs/AESI/EOSI and hypoglycemia (if any) are reported
- The following laboratory testing (by the central laboratory):
 - FPG (all visits)
 - BHB (all visits except Visit 11)
 - HbA1c (all visits)
 - Clinical chemistry, including amylase and lipase (all visits)
 - Hematology (Visits 6, 11, 13, and 14 only)
 - Fasting lipids (Visits 6, and 12 only)
 - Urine pregnancy testing for WOCBP (all visits)
 - Pre-dose plasma concentration samples are collected and sent to the appropriate laboratory (Visits 8, 12, and 13 only)
 - Markers of calcium metabolism (Visits 6 and 13 only)
 - Urinalysis (dipstick and microscopy) (Visits 6 and 13 only)
 - Overnight urine collection for albumin, protein, creatinine, calcium, phosphorus, magnesium, glucose, and albumin-creatinine ratio (Visits 6, 11, and 13 only)

█ [REDACTED]

█ [REDACTED]

- PRO: PQAT (Visit 12 only)
- PRO: TRIM-D (Visits 6, 12, 13, and 14 only)
- 12-lead ECG (Visits 6 and 13 only)
- Patients are instructed to return to the site in the fasting state for their next visit (all visits except Visits 6 and 8, which precede telephone visits). They should be reminded to record in the diary the date and time of IMP intake on the day before their next visit (reminder at Visits 7, 11, and 12 only).
- For accountability and compliance purposes, patients are instructed to return to the site with their unused, in-use, and used wallets and pens at the next on-site visit (all visits).

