1.2 STUDY FLOW CHART

	Screening Period					Double-Blind Treatment Period ^a										FU Period
	Screening	Run-in (Lantus titration, single-blind placebo Run-in)				No titration of Lantus (except for safety)						Lantus titration permitted				
VISIT	1	2	3 ^b	4 ^b	5	6	7 ^b	8	9 ^b	10	11	12	13	14	15	16 ^c
Week	-6	-4	-3	-2	-1	0	2	4	6	8	12	18	26	39	52	54
Day (window [days])	-42	-28 (±3)	-21 (±2)	-14 (±2)	-7 (±2)	1 (-)	14 (±3)	28 (±3)	42 (±3)	56 (±3)	84 (±3)	126 (±3)	182 (±3)	273 (±7)	364 (±7)	378 (±3)
Informed consent	X															
Inclusion criteria	X															
Exclusion criteria	X	X	X	X	X	X										
Demographics	X															
Medical/Surgical History	X															
Medication History	X															
Body weight, height ^d	X	X			X	X		X		X	X	X	X	X	X	X
Vital signs ^e	X	X			X	X		X		X	X	X	X	X	X	X
Physical Examination:																
Complete	X												X			
Abbreviated ^f		X			X	X		X		X	X	X		X	X	X
Concomitant Medication	X	X			X	X		X		X	X	X	X	X	X	X
Diet & exercise instruction		X			X	X							X		X	
Instruction on basic GU hygiene & hydration					X	X		X		X	X	X	X	X	X	
Interactive response technology (IRT) contact	X	X				X		X		X	X	X	X	X	X	X

	Screening Period					Double-Blind Treatment Period ^a										FU Period
	Screening	Run-in (Lantus titration, single-blind placebo Run-in)				No titration of Lantus (except for safety)						Lantus titration permitted				
VISIT	1	2	3 ^b	4 ^b	5	6	7 ^b	8	9 ^b	10	11	12	13	14	15	16 ^c
Week	-6	-4	-3	-2	-1	0	2	4	6	8	12	18	26	39	52	54
Day (window [days])	-42	-28 (±3)	-21 (±2)	-14 (±2)	-7 (±2)	1 (-)	14 (±3)	28 (±3)	42 (±3)	56 (±3)	84 (±3)	126 (±3)	182 (±3)	273 (±7)	364 (±7)	378 (±3)
Randomization						X										
Dispense glucose meter, Beta-hydroxybutyrate (BHB) meter		X														
Dispense glucose test strips and BHB strips		X				X	X	X		X	X	X	X	X	X	
Measurement of capillary BHB at the site						X	X	X		X	X	X	X	X	X	
Dispense diary	X	X				X	X	X		X	X	X	X	X	X	
Collect/review diary		X			X	X	X	X		X	X	X	X	X	X	X
Instruction on diabetic ketoacidosis symptoms, glucose testing		X			X	X	X	X		X	X	X	X	X	X	
Dispense IMP and Lantus		X				X	X	X		X	X	X	X	X	X	
IMP and Lantus accounting & compliance					X	X	X	X		X	X	X	X	X	X	
Review results of SMBG and recommend Lantus dose adjustments as necessary ^g		X	X	X	X	X	X	X	X	X	X	X	X	X	X	X
Record results of a 7-point SMBG ^h						X						X			X	
12-lead ECG ⁱ	X					X							X			

	Screening Period					Double-Blind Treatment Period ^a											FU Period

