- a If a patient discontinues treatment with IMP early during the Treatment Period, the patient will have a Premature EOT Visit, and a Follow-up Visit 2 weeks after the last dose of IMP. However, every effort will be made to have the patients return to the site for all scheduled visits, in particular the visits at Week 18 (Visit 12) and Week 52 (Visit 15). If the patient does not agree to a site visits, the patient will be contacted by telephone to inquire about safety status. If a patient discontinues (or completes) treatment and study at the same time, a single visit for both EOT and EOS will be performed.
- b To ensure effective Lantus dose titration during the Run-in Phase, patients will be instructed to call the Investigator to discuss the necessary adjustments in Lantus dose if they have 2 or more SMBG measurements above 100 mg/dL or below 80 mg/dL.
- c Two weeks after the last dose of IMP.
- d Height to be measured only at Screening.
- e Vital sign measurements (sitting blood pressure [BP], heart rate): 3 separate seated BP and heart rate measurements should be taken with at least 1 minute between readings, following a 5-minute rest period and prior to phlebotomy (if applicable).
- f The abbreviated physical exam should focus on cardiac and respiratory systems, as well as any areas important for assessment of AEs if necessary.
- g Fasting (pre-breakfast/pre-injection if available) SMBG: during the 4-week Run-in Lantus titration period, fasting SMBG should be performed daily. Thereafter, the number of fasting SMBG checks can be reduced according to the Investigator's judgment, however at least 3 fasting (pre-breakfast) SMBG measurements per week should be done from Weeks 0 to 18 and 3 measurements during the week prior to study visits from Weeks 19 to 52 (Section 8.2.1.4). Patients will review SMBG values with site staff either at site visits, phone visits or extemporaneously if patient feels high or low SMBG values may necessitate a dose adjustment. See Table 2 for permitted adjustments. Patients should be advised to check SMBG whenever they experience any symptoms of hypoglycemia, if possible, before taking the treatment. **Note:** Units in table represent plasma glucose values as glucometers used for SMBG display results already adjusted to plasma concentration and no conversion is required.

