4.4 RATIONALE FOR STUDY DESIGN AND CONTROL GROUPS

This study is designed to assess the efficacy and safety of sotagliflozin (compared to placebo) when used as add-on therapy to basal insulin (Lantus), alone or in combination with oral antidiabetes drugs (OADs). Patients will be switched from their current basal insulin to Lantus (1:1 dose conversion, or 20% reduction if on treatment with Toujeo or Neutral Protamine Hagedorn [NPH] twice daily) and will have a 4-week dose titration period to improve their basal insulin dose prior to Randomization, utilizing a standard titration algorithm. During this period, compliance with the algorithm will be reviewed by an internal group blinded to the treatment assignment and investigators will be contacted as needed to encourage adherence to titration algorithm. During this Lantus titration period, the dose of concomitant OADs should stay unchanged, except if decreases are needed due to hypoglycemia.

The primary endpoint is HbA1c reduction from Baseline to Week 18 because it is expected that sotagliflozin can provide significant additional glycemic efficacy even in an advanced T2D population with presumed beta cell failure. During the first 18 weeks no adjustment of Lantus is permitted (except for safety reasons or if rescue criteria are met) to enable the assessment of the effect of randomized treatment drug on top of a stable background therapy of insulin \pm OADs. After Week 18, titration of Lantus may resume following the same titration algorithm utilized during the Run-in period. This will enable the assessment of the effect of the randomized study drug in a context of total dose of insulin being simultaneously adjusted and more typical of a real-world setting. Prandial insulin or GLP-1 agonists will be the recommended rescue therapy for patients on a stable regimen of oral antihyperglycemic agents who cannot adequately achieve glycemic control by up-titrating their Lantus dose, as per international diabetes treatment guidelines (13, 14). However, the investigator will be allowed to choose from any antidiabetic agent (with the exception of the SGLT2 inhibitors class) according to their clinical judgment and in line with the local standard of care. The protocol stipulates that patients be provided rescue therapy according to increasingly stringent hyperglycemia criteria (based on FPG and/or HbA1c) as aligned with regulatory guidance (15).

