8.2.1.3 Dose titration and modification

Lantus will be titrated during the 4-week single-blind Run-in Phase and if necessary after 18 weeks of the core Treatment Period to reach and maintain the target fasting glucose.

The target range for fasting (pre-breakfast/pre-injection if available) blood glucose is 80-100 mg/dL (4.4 to 5.6 mmol/L) avoiding hypoglycemia.

During Run-in (Week -4 to Week -1): after initiating the study provided basal insulin, Lantus, the insulin dose will be up-titrated every 3 days (twice per week) until the patient reaches the target fasting blood glucose according to the recommended regimen (Table 2). The dose adjustments will be made in consultation with the study site either at site visits, phone visits, or unscheduled phone contacts. At the end of Run-in, patients with HbA1c $\geq 7.0\%$ measured at Visit 5 (Week -1) are eligible to be randomized to receive the IMP treatment (sotagliflozin 200 mg, sotagliflozin 400 mg or placebo) on top of Lantus.

During the randomized core Treatment Period (Weeks 0 to 18): no insulin titration should be implemented.

For patients with HbA1c $< 7.5\%$ measured at Week-1, a 10% reduction in the Lantus dose at the randomization may be considered by the Investigator as needed, to reduce a potential risk of hypoglycemia.

Lantus daily dose will remain stable ($< \pm 10\%$ from the dose at randomization, or $< \pm 4$ units, whichever is less) unless it is deemed necessary by the investigator to reduce or increase the dose for safety reasons (ie, severe hypoglycemia or AE/SAE) or the patient has met the hyperglycemic threshold for rescue therapy. In such a case, rescue assessment will apply and be implemented (Section 8.2.4). Increase and optimization in Lantus dose will be the first step of rescue therapy prior to initiation of prandial insulin or GLP-1 receptor agonists.

After the core Treatment Period (Weeks 19 to 52): if the target fasting SMBG level is not achieved at the end of Week 18, insulin dose should be continuously up-titrated to maintain the fasting SMBG in the target range until the EOT. Titration will be done on a weekly basis, or as frequently as deemed necessary by the Investigator.

Lantus dose adjustment is based on fasting SMBG values using study glucose meter that displays results already converted to plasma glucose concentration. Regular self-monitoring of plasma glucose is very important in order to achieve the blood glucose targets. It is recommended to

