8.2.1.4 Self-monitoring of blood glucose (SMBG)

Self-monitoring of blood glucose measured by patients will be used for investigators to guide Lantus dose modification and monitor for hypoglycemia or hyperglycemia.

A meter for self-assessment of blood glucose will be dispensed at the Week -4 Run-in visit (Visit 2). Patients will be trained on how to accurately measure plasma glucose values with the blood glucose meter. The study provided glucose meter will be used over the course of the study period. The investigator or site study staff will explain the need to measure glucose at the times requested for profiles and how to correctly record the values and times in the diary. Training is repeated as often as necessary at the study visits and the site study staff reviews the patient's diary at each on-site visit.

Patients will also receive a patient diary at all on-site visits with the exception of Visit 5 and Follow-up (Visit 16). The diary will be reviewed at all on-site visits from Visit 2 to Visit 16.

The performance of SMBG is outlined in [Table 3](#) and is also specified in [Section 1.2](#).

Table 3 – Instruction for SMBG performed during the study

SMBG	Definition	Frequency		Weeks/Visits
		Recommended	Mandatory	
Fasting SMBG	Overnight fasting pre-breakfast and before Lantus injection or any OAD intake	Daily until achieving fasting SMBG target	Daily SMBG	Week -4 to Week -1
		5 days per week	3 days per week	Week 0 to Week 18
		5 days per week until achieving fasting SMBG target	3 days during the week prior to study visit	Week 19 to Week 52
7-points	Before and 2 hours after breakfast, lunch and dinner, and bedtime	As needed	1 day during the weeks prior to Weeks 0, 18, and 52	Visit 6, 12, and 15

OAD = oral antidiabetes drugs; SMBG = self-monitored blood glucose.

Fasting SMBG readings will be used to guide the Lantus dose modification to reach and maintain the glucose targets. The investigators should review the SMBG records at each study visit including the phone visits so that they can provide instruction to the patients for appropriate insulin dose adjustment.

Fasting SMBG

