8.7.1 Treatment accountability and compliance

Accounting and compliance for IMPs and Lantus will be performed at Visit 5 and all subsequent on-treatment visits (excluding telephone visits).

The Investigator will check the compliance to the study treatments based on the patient diary and will then complete the appropriate site treatment and patient treatment log forms. Returned IMP and Lantus NIMP (unused, in-use, or used wallets and pens) should be counted by site staff. In addition, the dosing information will be recorded on the appropriate pages of the eCRF.

An internal group will review compliance with the fasting SMBG algorithm for Lantus titration in a blinded manner during the study. Mean fasting SMBG and insulin doses over time will be used to identify the out of the target values (within the range of 4.4 to 5.6 mmol/L [80-100 mg/dL]) via a pre-set program. The identified issues will be sent to the Investigators for their actions on the refinement of the titration schedule as needed.

For other NIMPs (metformin, and other OADs), name, start and end date of treatment, total daily dose, etc, will be documented in the source documents. Compliance to NIMPs will be checked by interviewing the patient and reviewing diary at each on-treatment visit and be documented in the source documents and in the eCRF.

If compliance is inadequate as determined by the Principal Investigator, patients will be trained again and mentored. If sub-optimal compliance continues after training and mentoring, patients may be discontinued at the discretion of the Investigator after discussion with the Sponsor's medical monitor.

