10.1.2.2 Telephone Visits 7 and 9 (Weeks 2 and 6)

The following will be performed at this visit:

- Fasting SMBG is assessed and Lantus dose adjustments are made as necessary
- AEs/SAEs/AESI/EOSI and hypoglycemia (if any) are reported
- Patients are evaluated for glycemic rescue (see [Section 9.1.4.7](#))
- Patients are instructed to return to the site in the fasting state for Visits 8 and 10.

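### The protocol's instructions on Lantus in Weeks 0 to 18 disagree with one another and need one rule and one list of exceptions

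*Protocol*

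**What the plan says.** **Text that holds the dose.** Section 8.2.1.3 states: "During the randomized core Treatment Period (Weeks 0 to 18): no insulin titration should be implemented". It keeps the daily dose within less than 10% or less than 4 units of the randomization dose, whichever is smaller, with exceptions for safety and for patients who reach the rescue threshold. It also lets the investigator consider a 10% reduction at randomization when Week -1 HbA1c is below 7.5%. Section 10.1.2 repeats the limit directly above the visit lists, and a flow chart column header (Section 1.2) bars titration except for safety. Section 4.4 gives the purpose: "to enable the assessment of the effect of randomized treatment drug on top of a stable background therapy of insulin".

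**Text without that limit.**
- Section 10.1.2.1, on-site visits: "Fasting SMBG is assessed and Lantus dose adjustments are made as necessary (all visits"
- Section 10.1.2.2, telephone Visits 7 and 9: "Fasting SMBG is assessed and Lantus dose adjustments are made as necessary"
- Flow chart row, ticked at every visit from 2 to 16: "Review results of SMBG and recommend Lantus dose adjustments as necessary"
- Flow chart footnote g, which covers SMBG in Weeks 0 to 18 among other phases: "See Table 2 for permitted adjustments". Table 2 is the algorithm for reaching a fasting value of 80-100 mg/dL.
- Section 8.2.1.4: "The investigators should review the SMBG records at each study visit including the phone visits so that they can provide instruction". The sentence before it links fasting readings to dose changes aimed at the glucose targets.

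**Sponsor review of titration.** Section 8.7.1 has an internal group look for out-of-target values over the course of the study, and then: "The identified issues will be sent to the Investigators for their actions on the refinement of the titration schedule as needed". Section 4.4 describes this review only for the four-week titration before randomization.

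**The concern.** The primary result is meant to show what the drug adds to insulin that is not moving. A site that works from the visit list or the flow chart row, rather than from Section 8.2.1.3, could change Lantus on fasting SMBG during the fixed-dose phase and believe it was following the protocol. Another site could leave the dose alone and believe the same.

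The analysis would not separate the two. Protocol Section 11.4.2.1 uses all Week 18 HbA1c values, including those after rescue. SAP Section 2.1.3 identifies Lantus rescue partly from an eCRF item asking whether the dose was per protocol or rescue, so a change made under the visit list could be recorded as per protocol. SAP Section 2.4.4.3 summarizes Lantus dose by visit and arm. That would reveal average drift but would not correct for it, and no sensitivity analysis for Lantus changes in Weeks 0 to 18 is specified.

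**Working it through.** **1. Which contacts are affected.** Visit 6 is a special case, because Section 8.2.1.3 itself allows a reduction there. Visit 12 is the boundary, because titration resumes after it. The contacts that lie clearly inside the fixed-dose phase are on-site Visits 8, 10 and 11 (Weeks 4, 8 and 12) and telephone Visits 7 and 9 (Weeks 2 and 6).

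**2. Whether the bullet can only mean safety or rescue.** The text does not settle this.
- The same instruction is used at run-in Visits 2 and 5, where titration is intended.
- Rescue evaluation and hypoglycemia reporting are separate bullets at the same visits.
- Other items in the Section 10.1.2.1 list are restricted to named visits; this one is marked for all.

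**3. Exceptions named for the fixed-dose phase.**

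| Place in the protocol | Safety | Rescue |
|---|---|---|
| Summary, list of trial periods | yes | not named |
| Flow chart column header | yes | not named |
| Summary, Lantus dose paragraph | not named | yes |
| Section 6.1.2 | not named | yes |
| Sections 4.4, 8.2.1.3 and 10.1.2 | yes | yes |

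The safety exception itself also differs. Section 8.2.1.3 introduces it as a definition (severe hypoglycemia, or an AE or SAE). Section 10.1.2 introduces it by example and names hypoglycemia without the severity qualifier.

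**4. What dilution would do to power (illustration only).** Inputs from Protocol Section 11.1: SD 1.2, two-sided 5% test, 280, 140 and 140 patients, differences of 0.5 (400 mg) and 0.4 (200 mg).

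Formula: power = Φ(difference / SE − 1.96), with SE = 1.2 × √(1/n₁ + 1/n₂).

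- 400 mg: SE = 1.2 × √(1/280 + 1/140) = 0.1242. At 0.5: Φ(4.025 − 1.96) = 98.1%, which meets the stated floor of 95%.
- 200 mg: SE = 1.2 × √(2/140) = 0.1434. At 0.4: Φ(2.789 − 1.96) = 79.6%, which agrees with the stated 80%.

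Assumed dilution of the planned difference:

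| Dilution | 400 mg difference | Power | 200 mg difference | Power |
|---|---|---|---|---|
| 0% | 0.50 | 98.1% | 0.40 | 79.6% |
| 10% | 0.45 | 95.2% | 0.36 | 70.9% |
| 20% | 0.40 | 89.6% | 0.32 | 60.7% |

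The 400 mg comparison stays at 95% power down to a difference of (1.960 + 1.645) × 0.1242 = 0.448, a dilution of about 10%. The 200 mg comparison starts at its target and has no reserve.

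**The case against.** The strongest reply is that the limit already governs the quoted bullets. They are subsections of Section 10.1.2, whose opening text holds the dose until after Week 18. The flow chart header stands over the row that carries footnote g. Table 2 sits inside Section 8.2.1.3, so the footnote leads a site to the section with the restriction. Section 8.2.1.3 (additional item 2) and Section 8.2.4 place titration in the run-in and after Week 18. Some adjustment wording is also needed in Weeks 0 to 18, because a Lantus increase is the first rescue step and rescue is evaluated at those visits. The phone visits mentioned in Section 8.2.1.4 include run-in Visits 3 and 4. Section 8.7.1 reviews compliance with a titration algorithm, and arguably none applies in the fixed-dose phase.

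Much of this stands. A careful site can read the bullets within the limit, and Section 8.7.1 does not expressly ask for changes in Weeks 0 to 18. It does not remove the inconsistency. Section 8.2.4 also contains a bullet asking, with no phase limit, that basal insulin be titrated by the algorithm. The time span of the sponsor's review still differs between Sections 8.7.1 and 4.4, and the exceptions still disagree.

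A reader might go further and infer that the protocol orders treat-to-target titration in Weeks 0 to 18, that increases would fall mainly on placebo, and that the primary difference would shrink by a definite amount. The documents do not support that. More increases on placebo and more reductions on active drug are plausible, since sites see fasting SMBG, but patients in every arm may be above 80-100 mg/dL. Multiplying the largest Table 2 step by the number of contacts gives only a ceiling, and nothing in the documents converts units of insulin into HbA1c.

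**Conclusion.** The inconsistency is real and should be resolved. It concerns wording: the fixed-dose intention is clear in Sections 4.4, 8.2.1.3 and 10.1.2, but the operating text does not carry it through and the exceptions are not uniform. The likely consequences are variation between sites and a less clean estimate of effect on stable insulin. Dilution of the Week 18 difference is plausible but unquantified, and the documents state neither its size nor its direction. If it occurred, it would be conservative for superiority. The power figures rest on the plan's own SD and differences and on assumed dilution; they show sensitivity, not an expected loss. On that basis the 400 mg comparison has some reserve and the 200 mg comparison has none.

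**What to change.** Reconcile Sections 10.1.2.1, 10.1.2.2, 8.2.1.4 and 8.7.1, the flow chart row and footnote g with Sections 8.2.1.3 and 10.1.2, so that one stated rule and one stated list of exceptions govern Lantus in Weeks 0 to 18. Specifically:

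- Split the visit bullet by phase, and say what applies at Visits 6 and 12.
- State in which phases footnote g's pointer to Table 2 applies.
- State in Sections 8.7.1 and 4.4 in which phases the out-of-target review and the queries to investigators run.
- Use the same exceptions in the summary, the flow chart header and Sections 4.4, 6.1.2, 8.2.1.3 and 10.1.2, and make the safety wording agree.
- Carry the result into the flow chart copied in SAP Appendix D.

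Which clinical rule and which exceptions apply is for the sponsor to decide. The cost is protocol wording, a memo to sites and, if the review is limited to certain phases, a date filter in the titration-monitoring program. No new visits or data are needed.
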